6.4 Statistical Hypotheses

6.4.1 Coprimary Immunogenicity Endpoints

The study is a multicenter, randomized, two-arm, active-controlled study to evaluate PXVX0317 vaccine vs. placebo. A successful trial means success on each of the coprimary endpoints: seroresponse (H_{A1}), GMT (H_{A2}), and lot consistency pairwise GMT ratios (H_{A3} , FDA only), all at Day 22 using the IEP. Statistical hypotheses for each of these endpoints are discussed in turn in this section. The familywise error rate is fixed at a two-sided alpha of 0.05 by the requirement that all coprimary endpoints must be met for a successful outcome.

In standard statistical notation, the null and alternative hypotheses are:

H₀: H_{A1} not met or H_{A2} not met or H_{A3} not met

H_A: H_{A1} met and H_{A2} met and H_{A3} met

where H_{A1} , H_{A2} , and H_{A3} are the alternative hypotheses for each of the coprimary endpoints as defined below in this section. Note: H_{A3} being met is only required for FDA.

The first coprimary endpoint is the treatment group-specific estimates and difference between treatment groups in anti-CHIKV SNA seroresponse rates using a titer of at Day 22 in the IEP for all age strata pooled and is tested in two ways. First, the lower bound of the Newcombe hybrid score method two-sided 95% CI on the difference in seroresponse rates between PXVX0317 and placebo must be secondly, the null hypothesis of no difference between seroresponse rate percentages is tested using a two-sided chi-square test with alpha=0.05. In standard statistical notation, the null and alternative hypotheses for the first coprimary endpoint are as follows:

H₀₁: $(P_{PXVX0317} - P_{placebo})$ or $(P_{PXVX0317} - P_{placebo}) \leq 0$ using a two-sided chi-square test

 H_{A1} : $(P_{PXVX0317} - P_{placebo})$ and $(P_{PXVX0317} - P_{placebo}) > 0$ using a two-sided chi-square test

where $P_{PXVX0317}$ is the percentage of PXVX0317 participants and $P_{placebo}$ is the percentage of placebo participants with seroresponse at a titer of at 21 days after vaccination in the IEP for all age strata pooled.

The second coprimary endpoint tests for a significant difference in treatment group-specific Day 22 GMTs in the IEP for all age strata pooled, as derived from a one-sided alpha=0.025

ANOVA with log₁₀-transformed anti-CHIKV SNA titers (log₁₀) as the dependent variable and treatment group and study site as the fixed effects. The adjusted least square means and their 95% CIs calculated based on the ANOVA are back-transformed and reported as the group GMT values. In standard statistical notation, the null and alternative hypotheses are:

H₀₂: $(GMT_{PXVX0317} - GMT_{placebo}) \leq 0$

HA2: $(GMT_{PXVX0317} - GMT_{placebo}) > 0$

where GMT_{PXVX0317} is the GMT 21 days after vaccination for IEP participants in all age strata pooled.

The third coprimary endpoint tests the pairwise GMT ratios at Day 22 of consecutively manufactured lots (A:B, B:C, A:C) for equivalence using two one-sided tests with alpha=0.025 each in the IEP for adults 18 to <46 years of age. Pairwise GMT ratios are derived from an ANOVA model with log₁₀-transformed anti-CHIKV SNA titers as the dependent variable and vaccine lot and study site as fixed effects. Lot-to-lot consistency is demonstrated if the two-sided 95% CI of the GMT ratio is within [0.667; 1.5] for all pairs of vaccine lots. In standard statistical notation, the null and alternative hypotheses are:

H₀₃: $(GMT_{PXVX0317 \text{ lot } A}/GMT_{PXVX0317 \text{ lot } B}) < 0.667 \text{ or}$

 $(GMT_{PXVX0317 \text{ lot } A} / GMT_{PXVX0317 \text{ lot } B}) > 1.5 \text{ or}$

 $(GMT_{PXVX0317 lot B}/GMT_{PXVX0317 lot C}) < 0.667 or$

 $(GMT_{PXVX0317 \text{ lot } B}/GMT_{PXVX0317 \text{ lot } C}) > 1.5 \text{ or}$

 $(GMT_{PXVX0317 \text{ lot } A} / GMT_{PXVX0317 \text{ lot } C}) < 0.667 \text{ or}$

 $(GMT_{PXVX0317 lot A}/GMT_{PXVX0317 lot C}) > 1.5$

H_{A3}: (GMT_{PXVX0317 lot A}/ GMT_{PXVX0317 lot B}) \geq 0.667 and

 $(GMT_{PXVX0317 \mbox{ lot }A}/\mbox{ }GMT_{PXVX0317 \mbox{ lot }B}) {\leq} 1.5$ and

 $(GMT_{PXVX0317 \mbox{ lot }B}/\mbox{ }GMT_{PXVX0317 \mbox{ lot }C}) \!\geq\!\! 0.667$ and

 $(GMT_{PXVX0317 \text{ lot }B}/GMT_{PXVX0317 \text{ lot }C}) \leq 1.5 \text{ and}$

 $(GMT_{PXVX0317 \text{ lot } A}/GMT_{PXVX0317 \text{ lot } C}) \ge 0.667 \text{ and}$

 $(GMT_{PXVX0317 \text{ lot } A}/GMT_{PXVX0317 \text{ lot } C}) \leq 1.5$

where GMT_{PXVX0317 lot X} is the GMT at 21 days after vaccination for IEP participants receiving PXVX0317 Lot A, B or C. Note that success on the Day 22 lot consistency endpoint is only required for FDA.

6.4.2 Key Secondary Immunogenicity Endpoints

A prespecified hierarchical approach is employed for the seroresponse key secondary immunogenicity endpoints to preserve the type I error rate without the need for further multiplicity adjustment. If the null hypotheses are rejected for all coprimary endpoints, only then are the key secondary endpoints for the seroresponse rate difference (H_{A4}) at Days 15, 183, and 8 tested sequentially, in that order, each for the IEP across all age groups combined.

At Day 15, the endpoint is tested for the success criterion of the lower bound of the two-sided Newcombe hybrid score method 95% CI on the difference in seroresponse rates between PXVX0317 and placebo and superiority to placebo is tested using a two-sided chi-square test with alpha=0.05. At Day 183 and Day 8, only superiority to placebo using a two-sided chi-square test with alpha=0.05 is tested. When a nonsignificant test is reached formal testing stops, and the remaining endpoints are reported for information only.

- 1. Day 15 seroresponse at a titer of **and** including superiority to placebo and the success criterion of the lower bound of the two-sided Newcombe hybrid score method 95% CI on the difference in seroresponse rates between PXVX0317 and placebo **and**.
- 2. Day 183 seroresponse at a titer of **series** including superiority to placebo.
- 3. Day 8 seroresponse at a titer of including superiority to placebo.

In standard statistical notation, the null and alternative hypotheses are:

H₀₄: $(P_{PXVX0317} - P_{placebo}) \leq 0$ using a two-sided chi-square test for Day 15 and $(P_{PXVX0317} - P_{placebo}) \leq 0$ using a two-sided chi-square test for Day 183 and Day 8.

H_{A4}: ($P_{PXVX0317} - P_{placebo}$) and ($P_{PXVX0317} - P_{placebo}$) >0 using a two-sided chi-square test for Day 15 and ($P_{PXVX0317} - P_{placebo}$) >0 using a two-sided chi-square test for Day 183 and Day 8.

After testing the coprimary immunogenicity endpoints and, if all met, the hierarchical key secondary immunogenicity endpoints, no other formal hypothesis testing is carried out. The remaining secondary immunogenicity endpoints involving GMTs, GMFI, other titers, the exploratory endpoint, and all safety endpoints are evaluated and reported for information only, thus no further Type I error control or multiplicity adjustment is needed.

6.5 Handling of Missing Data and Other Data Issues

Please see Section 6.3 for assumptions for AEs with missing relatedness and/or severity.

6.5.1 Missing or Partial Dates for Solicited Adverse Events

Solicited adverse events are collected from IP administration on Day 1 until Day 8 using an electronic diary (e-diary) or backup paper diary. In the case where a participant has all eight diary entries present and a single entry is missing a date (or has a partial date), then the missing date is assumed to be the date of the missing diary entry for that participant.

6.5.2 Missing or Partial Dates for Unsolicited Adverse Events and Concomitant Medications

Unsolicited AE collection begins at Day 1 (baseline), the day of IP administration. *Consequently, all AEs will be considered treatment-emergent regardless of onset date.*

For missing or partial dates for prior or concomitant medication/therapy, the following conventions are used for the purpose of determining whether the medication/therapy is concomitant or not. Original values are provided in the listings as is, without imputation.

- For start date missing completely or missing the year, impute the date to the date of first exposure to any study treatment.
- For start date missing both the month and the day, if the year is the same as the date of first exposure to any study treatment, impute the date to the date of first exposure to any study treatment, otherwise, impute the date to January 1st.
- For start date missing the day only, if the year and the month are the same as the date of first exposure to any study treatment, impute the date to the date of first exposure to any study treatment, otherwise, impute the date to the first of the month.
- For end date missing completely or missing the year, impute the date to the date of last contact.
- For end date missing both the month and the day, if the year is the same as the date of last contact, impute the date to the date of last contact, otherwise, impute the date to December 31st.
- For start date missing the day only, if the year and the month are the same as the date of last contact, impute the date to the date of last contact, otherwise, impute the date to the last day of the month.

6.5.3 Missing Outcome and Covariates

Participants are included in the analyses to the extent of their available data; missing immunogenicity data are not imputed. See Sections 5.5 and 5.7 and definition of anti-CHIKV human SNA assay titer in Section 6.3.

Participants with missing categorical data are counted in missing or unknown categories when appropriate. Participants with missing numeric data are treated as missing completely at random when calculating summary statistics. For likelihood-based analyses (e.g., regression), missing at random is assumed.

6.5.4 Non-Quantifiable Laboratory Data

Not applicable.

6.5.5 Implausible Participant Reported Outcomes

Values measured and reported by the participant directly (e.g., via the electronic or paper diary) are not corrected in a reconciliation process. In cases where the reported values are clearly biologically implausible, the reported values and associated toxicity grades are set to missing and excluded from analysis. These reported values are included in listings.

Example: Body (oral) temperatures less than $\leq 33^{\circ}$ C or $\geq 42^{\circ}$ C.

6.6 Adjustment for Covariates

Beyond the inclusion of site in the immunogenicity ANOVA models described in Section 6.1 and the additional inclusion of baseline log-transformed anti-CHIKV SNA titer as a covariate in the ANCOVA model if the baseline seropositive (anti-CHIKV SNA titer \geq LLOQ) rate is

 \geq 10%), no further adjustment for covariates is performed. Immunogenicity analyses are conducted for all age strata pooled as well as by separate age strata.

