3 STUDY DESIGN

3.1 Study Description

This is a phase 3 randomized, placebo-controlled, double-blind, parallel-group design with four treatment groups. Participants will be randomized in a 2:2:2:1 ratio within each of the three age strata (ages 12 to <18, 18 to <46, and 46 to <65) to receive one of three consecutively manufactured lots of PXVX0317 or placebo. With 3150 participants enrolled, the treatment group totals are estimated as follows:

- Group 1- PXVX0317 lot A: n=900
- Group 2- PXVX0317 lot B: n=900
- Group 3- PXVX0317 lot C: n=900
- Group 4- Placebo: n=450

A nested lot consistency sub study will be performed in adult participants 18 to <46 years of age in the PXVX0317 treatment groups (lot A, lot B, and lot C).

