3.1.2 Number of Participants (Planned)

At least 3150 enrolled healthy US adolescent and adult participants ages 12 to <65, stratified in three age groups: 12 to <18, 18 to <46, and 46 to <65 years of age. Enrollment will target at least 245 participants (210 PXVX0317 participants and 35 placebo participants) into the youngest and oldest age groups (12 to <18 and 46 to <65 years of age, respectively). The middle age group must include at least 1050 participants to provide adequate power for the lot consistency analysis.

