2.2 Study Design and Conduct

This is a phase 3 randomized, placebo-controlled, double-blind, parallel-group design with four treatment groups. Participants are randomized in a 2:2:2:1 ratio within each of the three age strata (ages 12 to <18, 18 to <46, and 46 to <65) to receive one of three consecutively manufactured lots of PXVX0317 or placebo. With 3150 participants enrolled, the treatment group totals are estimated as follows:

- Group 1- PXVX0317 lot A: n=900
- Group 2- PXVX0317 lot B: n=900
- Group 3- PXVX0317 lot C: n=900
- Group 4- Placebo: n=450

A nested lot consistency sub study is performed in adult participants 18 to <46 years of age in the PXVX0317 treatment groups (lot A, lot B, and lot C).

This multicenter study is conducted in the US, using approximately 50 sites. At least 3150 healthy US adolescent and adult participants ages 12 to <65 are enrolled, stratified in three age groups: 12 to <18, 18 to <46, and 46 to <65 years of age. Enrollment targets at least 245 participants (210 PXVX0317 and 35 placebo participants) into the youngest and oldest age groups (12 to <18 and 46 to <65 years of age, respectively). The middle age group must include at least 1050 participants to provide adequate power for the lot consistency analysis.

The per participant estimated total study duration is 212 days. The screening window is no greater than 30 days prior to Day 1 (randomization and administration of investigational product [IP]). Screening assessments include informed consent (and assent for adolescent participants 12 to <18 years of age), review of eligibility criteria, medical history, prior and concomitant medications, demography, physical examination including height and weight for body mass index calculation, vital signs, follicle-stimulating hormone (FSH) or serum pregnancy test for female participants, urine toxicology screening per investigator's discretion and viral markers for hepatitis B surface antigen (HBsAg), hepatitis C (HCV) and human immune deficiency virus 1 and 2 (HIV-1/HIV-2).

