6.1.2 Geometric Mean Titers and Geometric Mean Fold Increase

The superiority of PXVX0317 vaccine immunogenicity over that of placebo is explored further by comparing Day 22 GMTs derived from a linear model with a one-sided alpha=0.025. The primary model is an analysis of variance (ANOVA), with log₁₀-transformed anti-CHIKV SNA titers (log₁₀) as the dependent variable and treatment group and study site as the fixed effects in the model. No interaction term is used. The adjusted least square means and their 95% CIs calculated based on the ANOVA are back-transformed and reported as the group GMT values. No adjustment for multiplicity is applied. See Section 6.4 for statistical hypothesis, Section 6.9 for multiplicity considerations, and Section 8.4.1.2 for analysis outputs. Identical methods are used for treatment group comparison of GMTs at Days 8, 15, and 183.

Similar methods are applied to test for a significant difference between anti-CHIKV SNA GMTs at Day 22 for PXVX0317 and placebo if the baseline seropositive (SNA titer \geq LLOQ) rate is \geq 10% in the mITT population only, with baseline log-transformed SNA titer as a covariate in the ANCOVA model.

GMFI from baseline (Day 1) to Days 8, 15, 22 and 183 is calculated using the difference from Day 1 in log₁₀-transformed titers as the dependent variable in the ANOVA model. The adjusted least square means and their 95% CIs calculated based on the ANOVA are backtransformed and reported as the group GMFI values. The median, minimum and maximum titers and fold-increases are based on the non-transformed scale.

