6.7 Multicenter Study

This study is expected to enroll 3150 participants at up to 50 sites in US. Data from all sites are pooled, but site is a covariate in the immunogenicity ANOVA models described in Section 6.1.

Except for lot consistency analyses, PXVX0317 lots are pooled as the PXVX0317 treatment group.

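### The pooled-age GMT and GMFI models leave out age stratum, the only stated randomization stratifier; if age predicts titer, the vaccine-placebo contrast is slightly less precise than it could be, and no superiority conclusion changes

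*SAP*

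**What the plan says.** Protocol 3.1 states: "Participants will be randomized in a 2:2:2:1 ratio within each of the three age strata". SAP 2.2 repeats this, and neither document names another stratifier. Stratum sizes are given only as minimums: 245 in each outer group and, for the middle group, "The middle age group must include at least 1050 participants" (Protocol 3.1.2).

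The Day 22 GMT comparison over all ages is coprimary. SAP 6.1.2 specifies an ANOVA on log10 titer with "treatment group and study site as the fixed effects in the model. No interaction term is used", and SAP 6.4.1 uses the same terms. Protocol 8.3.1, 8.6.1.2 and 8.6.2.5.1 agree. GMFI uses this ANOVA with the change in log10 titer as response. SAP 6.7 confirms that "site is a covariate in the immunogenicity ANOVA models". SAP 6.6 adds only baseline titer, in an ANCOVA run if baseline seropositivity reaches 10%, and otherwise "no further adjustment for covariates is performed".

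What is reported is by group: the adjusted LS means and their 95% CIs "are back-transformed and reported as the group GMT values". The SAP does not state the weights behind those LS means. Separate analyses within each age stratum are planned.

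**The concern.** The model adjusts for site, which is not a stated stratifier, and omits the factor that is. No reason is given. Because allocation is balanced within age strata, leaving age out does not bias the contrast. But any between-age variation in titer that site does not absorb stays in the residual and inflates the model standard error of the vaccine-placebo difference. The by-age analyses do not change the pooled model.

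What is at stake is some precision on a coprimary comparison. The Day 8, 15 and 183 GMTs and GMFI share the model but are reported for information only. In the IEP every baseline is below LLOQ and set to LLOQ/2, so GMFI there is the GMT divided by a constant, and the same standard errors apply.

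**Working it through.** **The plan's own figure.** The documents give no power or interval width for the pooled GMT model. The only figure built on the log10 SD is lot-consistency power (SAP 4.2): 2Φ(0.176 / (0.455·√(2/207)) − 1.96) − 1 = 2Φ(1.975) − 1 = 95.2%, against 95% stated. So SD 0.455 is a fair input.

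**Inputs.** From the documents: SD 0.455; 2430 vaccine and 405 placebo evaluable (SAP 4.1), hence 6:1 in each stratum; values below LLOQ set to LLOQ/2 (SAP 6.3). Assumed: outer groups shifted by +s and −s log10 from the middle group, s = 0.1 to 0.3, in vaccine recipients only; placebo constant; strata 245/2660/245 (outer groups at their minimum) or 1050 each (middle group at its minimum).

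**Formulas.** Let f be the fraction of participants in the two outer groups (490/3150 = 0.156, or 0.667). Ignoring site:

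- Residual variance without age: (6/7)(0.455² + f·s²).
- With a common age term, the fitted shift is 6s/7. Residual variance: (6/7)·0.455² + (6/49)·f·s².
- SE of the contrast: residual SD × √(1/2430 + 1/405) = residual SD × 0.05367.
- Model SE of the vaccine group mean: residual SD / √2430.

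Example, equal strata, s = 0.3. Without age: (6/7)(0.2070 + 0.0600) = 0.2289, SD 0.478, SE 0.0257. With age: 0.1774 + 0.0073 = 0.1848, SD 0.430, SE 0.0231. The table also divides by residual degrees of freedom, which moves only the last digits.

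| Strata | s | Contrast SE, no age | With age | Cut | Vaccine-group SE, no age | With age |
|---|---|---|---|---|---|---|
| 245/2660/245 | 0.1 | 0.02270 | 0.02264 | 0.3% | 0.0086 | 0.0086 |
| 245/2660/245 | 0.2 | 0.02295 | 0.02267 | 1.2% | 0.0087 | 0.0086 |
| 245/2660/245 | 0.3 | 0.02337 | 0.02273 | 2.7% | 0.0088 | 0.0086 |
| 1050 each | 0.1 | 0.02298 | 0.02268 | 1.3% | 0.0087 | 0.0086 |
| 1050 each | 0.2 | 0.02403 | 0.02283 | 5.0% | 0.0091 | 0.0086 |
| 1050 each | 0.3 | 0.02569 | 0.02309 | 10.1% | 0.0097 | 0.0087 |

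**No age effect.** The term costs √(2833/2831) − 1 = 0.04% in SE.

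**Site in both models.** Simulated with 50 unequal sites, between-site SD 0.1 log10 (assumed) and 60 runs per setting, for s = 0.1 to 0.3. If sites share one age mix, the cut is 0.29% to 2.66% (245/2660/245) and 1.29% to 10.11% (equal strata). If site explains 17% of the age variance, it is 0.28% to 2.30% and 1.07% to 8.68%. If site explains 50%, it is 0.13% to 1.40% and 0.62% to 5.25%.

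**Equal-variance assumption.** With placebo constant, the sampling SE of the contrast, and of the vaccine mean, is 0.455/√2430 = 0.00923. The contrast SE with age (0.0226 to 0.0231) is still about 2.5 times that. Age removes only 0.5% to 4.5% (245/2660/245) or 2.2% to 15.8% (equal strata) of the excess. The vaccine-group SE errs the other way: without age it is below 0.00923 in five of the six settings, and with age it is 5% to 7% below in all six.

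**Superiority.** Taking the phase 2 GMT of 1712 (28 days after one dose) and LLOQ 15 (assumed), log10(1712/7.5) = 2.36. With LLOQ 40 (assumed), log10(1712/20) = 1.93. Dividing by the largest SE in the table, 0.0257, gives about 92 and 75, against 1.96.

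**The case against.** The strongest reply is that the plan does not promise the interval in question. The coprimary endpoint is a GMT with CI for each group, success is a significance test, and there is no stated CI for the unconditional Day 22 vaccine:placebo GMT ratio. For the group intervals that are reported, a common variance with placebo near LLOQ/2 already makes the vaccine interval too narrow in most settings, and an age term alone narrows it further. This stands. It limits the point to the contrast standard error and means that age should not be added by itself.

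It is also fair that no age effect is documented (the sponsor's phase 2 dose study enrolled only 18 to <46), that omitting age was prespecified, that age is examined separately, and that no decision turns on it. These set the priority. They do not explain why the pooled model carries site and not the stratifier.

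Equal age weights in the LS means would do harm. At s = 0.1 with 245/2660/245, the simulated half-width of the vaccine mean goes from 0.0169 to 0.0278, about 64% wider. If only the oldest group were 0.1 to 0.3 log10 lower, the reported vaccine GMT would fall 5% to 14% below the one at observed proportions (1 − 10^(−(1/3 − 245/3150)·(6/7)·0.1) = 5%; 14% at 0.3). The weights therefore have to be stated.

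**Conclusion.** The omission is a fact of both documents. Its consequence is conditional: if age predicts titer beyond what site absorbs, the model SE of the pooled vaccine-placebo contrast is larger than necessary, by the amounts tabulated and under the assumptions listed. If age does not predict titer, nothing is lost.

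A reader might infer three stronger things, and the documents support none of them:

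- That the coprimary test is invalid or biased. Allocation is balanced on age by design, the treatment estimate is the same with and without age, and there is no type I error inflation.
- That the published group GMT intervals are too wide. With placebo near LLOQ/2, the vaccine group interval is too narrow in most settings.
- That the gain could reach 11.9%. That needs placebo titers with SD 0.455 that also shift by 0.3 log10 with age. The seronegative-baseline rule, the LLOQ/2 rule and an expected placebo seroresponse under 5% make it unlikely.

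This is an optional improvement that changes no conclusion.

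**What to change.** - Add age stratum as a fixed effect, without interaction, to the pooled-age GMT and GMFI models in SAP 6.1.2, 6.4.1 and 6.6 and in Protocol 8.3.1, 8.6.1.2 and 8.6.2.5.1. Use the corrected age stratum, as SAP 6.3 already requires for immunogenicity analyses.
- In the LS means, weight age by the observed stratum proportions of the analysis population, pooled over arms. Set this by explicit coefficients, because a blanket observed-margins option would also re-weight site. The weights affect only the group GMTs, not the treatment contrast.
- Estimate residual variance separately by arm, so that a smaller residual does not further understate the vaccine GMT interval. Say how. If placebo is nearly constant, a fit weighted by arm variance would take the common age and site effects almost wholly from placebo. Keeping the least-squares estimates and using each arm's residual variance in the standard errors avoids this. The percentages above describe the planned common-variance model and do not add to what arm-specific variances already recover.
- Leave the seroresponse and lot-consistency analyses unchanged. The lot model is confined to ages 18 to <46 and omits no stratifier.

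The cost is 2 degrees of freedom out of about 2835, no new data, a SAP revision and a formal protocol amendment (Protocol 12.2) before unblinding. For so small a gain, it is best bundled with another amendment.
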